7.7 Unblinding

Unblinding procedure (which incorporates ICH E2A guidance, EU Regulations on clinical trials on medicinal products for human use and US Federal Regulations) is to unblind the report of any SAE that is unexpected and attributable/suspected to be attributable to the investigational product/product, prior to regulatory reporting. Causality will be determined by the investigator.

The IRB/REB will receive blinded or unblinded safety reports in keeping with local requirements. Suspected unexpected serious adverse reactions (SUSAR) reports will be distributed to the investigator and IRB/REB in compliance with local regulations.

The Medical Monitor will be responsible for the unblinding of events that meet the study stopping rules, if this is determined to be necessary for evaluation purposes by the data monitoring committee.

The blind should ordinarily be broken for regulatory submission.

Unblinding in case of an emergency is described below. However, it should be noted that is not anticipated that such occurrence will be encountered in the conduct of the study since it is unlikely that the knowledge of the vaccine received by the subject will affect his/her medical management.

The investigator may unblind a subject's treatment assignment **only in the case of an emergency**, when knowledge of the study treatment is essential for the appropriate clinical management or welfare of the subject. The unblinding should be formally completed in IWRS. Whenever possible, the investigator must first discuss options with the Study Medical Monitor or appropriate VBI study personnel **before** unblinding the subject's treatment assignment in IWRS. If this is impractical, the investigator must notify the Contract Research Organization (CRO) and sponsor as soon as possible, but without revealing the treatment assignment of the unblinded subject, unless that information is important for the safety of subjects currently in the study. The date and reason for the unblinding must be recorded in the appropriate data collection tool. If the Investigator does not have access to IWRS or is having technical issues, the

investigator can contact unblinded staff at the site for the treatment but this must be clearly documented in the source notes and should only be used as a back-up option.

For all other cases, the Medical Monitor will determine on a case-by-case basis if it is necessary to break the blind for safety purposes. The blind will be broken by the Medical Monitor or his designee for the specific subject. In the event that the blind is broken for a subject, the blind will be maintained for the clinical study team members to the extent possible to minimize the potential for introducing bias in evaluating the subject's data.

7.8 Stopping Rules

Stopping criteria for further study vaccinations in individual subjects:

The investigator will notify the sponsor (and/or sponsor representative) if any of the below conditions occur and will stop any further study vaccinations in an individual subject if they experience any of the following:

- Grade 4* post-injection reaction within 7 days after any study injection
- Clinically significant systemic reaction (i.e., angioedema, generalized urticaria) within 7 days after any study injection
- Grade 4** potentially life-threatening laboratory abnormality within 7 days after a study injection, irrespective of the study vaccine relationship (in clinical laboratory sub-study subjects)
- Grade 3 or 4* hypotension within 24 hours after any study injection
- Grade 3 or 4* respiratory reaction occurring within 24 hours after any study injection
- Any life-threatening event within 7 days after any study injection, regardless of relationship to study vaccine

*FDA Grading of Vaccine Reactions and FDA Grading of Vital Sign Abnormalities (Appendix 3)

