6.2.4 Sub-Studies

6.2.4.1 Clinical laboratory sub-study

At select study sites, clinical laboratory parameters (hematology, biochemistry) will be assessed one week after each vaccination with either Sci-B-Vac or Engerix-B® and compared to baseline (pre-vaccination) values, as part of a clinical laboratory sub-study. All subjects enrolled at these select sites will be required to come for three additional visits and to provide four additional blood samples, beyond those required for the main study. The clinical laboratory sub-study will include at least 10% of all subjects enrolled to the entire trial.

Blood samples for the clinical laboratory sub-study will be collected at baseline (Day 0, Visit 1) prior to receiving any study vaccine, and at each of the three additional visits (additional visits A1, A2 and A3 in Appendix 2 Schedule of Events), to be scheduled 1 week after each vaccination with Sci-B-Vac™ or Engerix-B® on Study Day 7 (-3/+7 days), Study Day 35 (-3/+7 days) and Study Day 175 (-3/+7 days), respectively. The following clinical laboratory parameters will be evaluated:

Hematology

- o White blood cell count with differential
- o Red blood cell count
- Hematocrit (HCT)

- Mean cell hemoglobin (MCH)
- Mean cell hemoglobin concentration (MCHC)
- Mean corpuscular volume (MCV)
- o Hemoglobin
- o Platelet count
- Biochemistry:
 - o Blood urea nitrogen (BUN), serum creatinine.
 - Alkaline phosphatase (AP), alanine transaminase (ALT), aspartate transaminase (AST), total and conjugated bilirubin, gamma-glutamyl-transferase (GGT)

Safety laboratory evaluations may be repeated if indicated (e.g. follow-up of a clinically significant laboratory abnormality (from baseline assessment))

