6.3.2 Vaccination visits

Vaccination will be done at Visit 1, 2 and 4 (Study Day 0, Study day 28 (-3 days/+7 days), and Study day 168 (+/- 7 days, respectively).

On Day 0 (Visit 1), subjects will have a blood sample collection prior to vaccine administration.

At subsequent vaccination visits (on Study Days 28 and 168), and prior to study vaccine administration, there will be a review of ongoing eligibility to receive the study vaccine and continue on the study. Diary cards will be collected (Study Day 28) and there will be a review of any local and systemic reactions. There will also be a blood sample collection prior to each vaccine administration.

Subject will remain at least 30 minutes after each vaccination to be observed for rare adverse reactions.

At each vaccination visit the following will be done:

Concomitant medications will be recorded, including other vaccines.

- A urine pregnancy test will be done in females of childbearing potential and reviewed prior to vaccination. Pregnancy test must be confirmed negative prior to study vaccine administration.
- Blood samples for Immunogenicity tests (measurement of anti-HBs, anti pre-S1 and anti pre-S2 levels and characteristics), on Study Day 0, Study Day 28 and Study Day 168 will be taken, prior to vaccination.
- Blood samples for assessment of clinical laboratory parameters will be taken on Study Day
 0, prior to vaccination (select sites).
- Vital signs will be assessed before and after the injection of study vaccine. Any abnormal vital sign after injection should be reassessed.
- Physical/History-directed physical examination will be done.
- Eligibility for receiving treatment will be reviewed by the investigator.
- Study vaccine will be administered.
- Subject will be monitored for 30 minutes after the injection.
- A diary card will be provided at each vaccination visit. In addition, at Visit 2 (Study Day 28), the diary card provided at Visit 1 will be collected and reviewed. Adverse events will be recorded in the eCRF.
- The next visit will be scheduled.
- Subjects will be reminded that they should return the diary card at the next visit and that
 they should not receive any inactivated vaccine 2 weeks prior to or 2 weeks following the
 first, second or third vaccination. Subjects will also be reminded not to have an attenuated
 vaccine between V1 (Study Day 0) and V2 (Study Day 28), or for 4 weeks after V2 or within
 4 weeks of the third vaccination on V4 (Study Day 168).

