7.2.3 Laboratory test abnormalities

In subjects participating in the clinical laboratory sub-study, abnormal laboratory test values will be recorded individually in an AE form if they qualify as AE (see Section 7.1.5) and are not part of the data supporting a medical diagnosis already reported as an AE. Any Grade 4 potentially life-threatening laboratory abnormality (see Appendix 4) within 7 days after a study injection will stop any further study vaccinations in the subject, irrespective of the study vaccine relationship, as defined in Section 7.8.

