7.9 Safety oversight

An independent Data Monitoring Committee (DMC) for this study will monitor human subject safety and consider study-specific data as well as relevant background information about the study vaccines, and target population under study.

The DMC will comprise of a minimum of 3 members. The DMC will operate under procedures that will be developed at the organizational meeting of the DMC. At this time, each data element that the DMC needs to assess will be clearly defined. The DMC will meet before the study starts or as soon thereafter as possible to discuss the protocol, set triggers for data review, define a quorum, establish guidelines for monitoring the study, and designate a DMC Chair.

All discussions and decisions will be documented in writing. The DMC will advise the study sponsor of its findings in writing.

In the event that a stopping rule for an individual subject is triggered (Section 7.8), the data monitoring committee will meet on an ad hoc basis to review the data and determine whether the clinical trial should be stopped or requires modification in order to proceed safely.

^{**}FDA Grading of Clinical Laboratory Abnormalities (Appendix 4)

The DMC will only meet if a stopping rule for an individual subject is triggered. In the event that a stopping rule is triggered, the DMC will make every reasonable attempt to meet as soon as possible, preferably within three (3) to five (5) business days of the Sponsor being notified of the event, but no later than ten (10) business days. During this period, the DMC will be provided the relevant information regarding the event(s) that triggered the stopping rule in the subject.

In the event that adequate information is not available in the timeframe noted above, the DMC may schedule a second meeting to review additional information regarding the event(s) triggering a stopping rule in an individual subject.

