- (h) NOCI: new onset of chronic illness
- (i) V3 should be scheduled at least 3 weeks after V2
- (j) V5 should be scheduled at least 3 weeks after V4
- (k) Blood sample collected 7 days (-3/+7 days) after vaccination

* Additional visits (A1, A2 and A3) required for study subjects at select sites participating in the clinical laboratory sub-study. A small subset of subjects participating in the clinical laboratory sub-study will be eligible to participate in an optional sub-study on cell-mediated immunity.

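### The Grade 4 laboratory stopping rule ends 7 days after an injection, but the sub-study samples that feed it may be drawn in window up to day 14

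*Protocol*

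**What the plan says.** **The rule.** Protocol 7.8 lists six criteria that stop further vaccination in an individual. One, for laboratory sub-study subjects only, is a "Grade 4 potentially life-threatening laboratory abnormality within 7 days after a study injection, irrespective of the study vaccine relationship". Section 7.2.3 repeats it: such a value "within 7 days after a study injection will stop any further study vaccinations in the subject". Another 7.8 criterion is "Any life-threatening event within 7 days after any study injection, regardless of relationship to study vaccine".

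**The samples.** Protocol 6.2.4.1 schedules A1, A2 and A3 on "Study Day 7 (-3/+7 days), Study Day 35 (-3/+7 days) and Study Day 175 (-3/+7 days), respectively", and the same sentence places each visit one week after a vaccination. Footnote (k) to the schedule in SAP 6.1 reads "Blood sample collected 7 days (-3/+7 days) after vaccination"; Appendix 2 of the protocol marks the same cells with (k). No other post-dose hematology or chemistry sample is scheduled. Repeat tests are allowed if indicated.

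**The doses.** Dose 1 is on Study Day 0. Protocol 6.3.2 places doses 2 and 3 on "Study day 28 (-3 days/+7 days), and Study day 168 (+/- 7 days, respectively").

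**The DMC.** Under 7.9 the committee meets ad hoc when an individual stopping rule is triggered. The section adds: "The DMC will only meet if a stopping rule for an individual subject is triggered". At its first meeting it is also to "set triggers for data review, define a quorum" and set guidelines for monitoring the study.

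**The concern.** The target sampling day is the last day that the rule covers, so the whole positive tolerance of the visit window lies beyond it. Two subjects with the same Grade 4 value, both sampled as the protocol allows, are treated differently according to the day of the draw. On day 7 the next dose is stopped whatever the cause and the DMC convenes. On day 8 neither follows from the rules.

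At stake is whether a mandatory safety rule acts on every result that its own schedule produces. For A1 and A2 this bears on whether the subject receives another dose. For A3, which follows the last dose, it bears only on whether the DMC is called.

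**Working it through.** The plan states no figure for this overlap, so the check sets the windows side by side.

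**Inputs**
- Rule: up to day 7 after an injection (Protocol 7.8, 7.2.3).
- Sampling: 7 days, -3/+7, after vaccination (SAP 6.1 footnote (k)).
- Dose 2: Study Day 28, -3/+7. Dose 3: Study Day 168, ±7 (Protocol 6.3.2).
- Sub-study: at least 10% of 1,564 subjects (Protocol 6.2.4.1, 9.1).

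**1. Overlap of rule and sampling**
- Earliest sample: 7 - 3 = day 4. Latest: 7 + 7 = day 14.
- Days 4 to 7 (4 permitted days) fall inside the rule; days 8 to 14 (7 permitted days) fall outside.
- So 7 of 11 permitted days are uncovered. This counts days. It is not a share of samples, since most draws may cluster near day 7.

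**2. Would a stop after a late sample still be useful?**
- Earliest dose 2: 28 - 3 = Study Day 25. Latest A1: 0 + 14 = Study Day 14. Gap: 25 - 14 = 11 days.
- Latest dose 2: 28 + 7 = Study Day 35. Latest A2: 35 + 14 = Study Day 49. Earliest dose 3: 168 - 7 = Study Day 161. Gap: 161 - 49 = 112 days.
- A3: no dose follows, so only the DMC step can be lost.

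**3. Does another provision close the gap?**
- The life-threatening-event criterion also ends at day 7. Under 7.1.2, life-threatening means at risk of death when the event occurs, which a Grade 4 number need not imply. In Appendix 4, for example, bilirubin above 1.75 x ULN with any raised liver test is Grade 4.
- Sections 6.1.2 and 6.3.2 require an eligibility review before each dose. They name no Grade 4 criterion, and no sub-study chemistry or hematology is scheduled at V2 or V4.
- Section 7.1.5 requires AE reporting of laboratory values that meet its conditions. Without symptoms, a therapy change or significant worsening from an abnormal baseline, that turns on the investigator's judgment. SAE reporting within 24 hours (7.3.1) is mandatory once an event is judged serious. Neither is a listed DMC trigger.
- Dating the abnormality rather than the sample does not help: a Grade 4 value that is only detected on days 8 to 14 cannot be placed at day 7 or earlier without an earlier sample.

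**4. Size of the group exposed to the gap**
- 0.10 x 1,564 = 156.4, so at least 157 subjects.
- Planned samples: 157 x 2 = 314 at A1 and A2, and 157 at A3. These are all planned samples, not affected ones. An affected subject needs both a draw after day 7 and a Grade 4 value, and the documents give neither the spread of sampling days nor a Grade 4 rate.

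**The case against.** **Seven days may be a deliberate acute-reaction window.** Four of the six criteria in 7.8 use 7 days and two use 24 hours. An automatic stop in a short window, with causality judged case by case afterwards, is a defensible pattern, and the target-day sample falls inside it. The consistency stands. As a rationale for this criterion it is weaker, because the rule applies whatever the relationship to vaccine, so it was not written to select plausibly related values, and the sampling aimed at day 7 has its tolerance mostly after that day.

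**A Grade 4 value on day 10 is not ignored.** This stands. A reader might infer that such a value goes unhandled or is left wholly to discretion. The documents do not support that: the pre-dose check and AE/SAE reporting are required processes, SAE forms notify the medical monitor automatically, and the monitor may request further tests. What is missing is narrower: a mandatory stop and a DMC review.

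**The gap might seem wider than 14 days.** Section 6.2.4.1 prints the windows in Study Days. Read literally, A2 could fall 42 - 25 = 17 days after dose 2 and A3 182 - 161 = 21 days after dose 3. The same sentence ties each visit to one week after vaccination, and footnote (k) counts from vaccination. The literal reading would also allow A2 on Study Day 32, 3 days before a dose 2 given on Study Day 35. The documents therefore support day 14 as the outer limit, and the larger figures should not be used.

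**The DMC may set further triggers.** It may, at its first meeting, but its procedures are not in the documents, and 7.9 as written confines its meetings to triggered stopping rules.

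**Few subjects may be affected.** Laboratory abnormalities of Grade 3 or above are excluded at screening, and no affected case can be shown. Both points stand and limit the weight of the concern.

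**Conclusion.** The mismatch holds as a minor point. In-window samples on days 8 to 14 fall outside the only mandatory laboratory stopping criterion, and no other provision requires a stop or a DMC meeting for a Grade 4 value found then. For A1 and A2 the stop would still precede the next dose, by at least 11 and 112 days. For A3 only the DMC step is lost.

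This rests on counting the windows from the actual vaccination and on taking the 7.9 meeting condition as written. The reach is the laboratory sub-study, at least 157 subjects, with no estimate possible of how many would be affected. A reader might take the 157 as affected subjects or suspect an effect on the trial's main conclusions. Neither follows: the 157 is the minimum sub-study size, and the gap does not touch the co-primary analyses.

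**What to change.** - In Protocol 7.8 and the matching sentence of 7.2.3, change 7 days to 14 days for the Grade 4 laboratory criterion only. Leave the other criteria as they are.
- In 6.2.4.1 and 6.3.6, state that the A1, A2 and A3 windows are counted from the actual vaccination date, as footnote (k) already does.

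A fixed limit of 14 days matches the sampling window, so it does not reach out-of-window draws or repeats after day 14. No visit, sample or measurement is added.

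The cost is one bullet, one matching sentence and a clarification in two sections. A few more subjects, some with unrelated Grade 4 values, may be stopped and referred to the DMC; the current rule already accepts that up to day 7. The laboratory criterion would then run longer than the clinical life-threatening-event criterion. That difference follows from when the samples are drawn, and a sentence saying so would be enough.

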7.9 Safety oversight

An independent Data Monitoring Committee (DMC) for this study will monitor human subject safety and consider study-specific data as well as relevant background information about the study vaccines, and target population under study.

The DMC will comprise of a minimum of 3 members. The DMC will operate under procedures that will be developed at the organizational meeting of the DMC. At this time, each data element that the DMC needs to assess will be clearly defined. The DMC will meet before the study starts or as soon thereafter as possible to discuss the protocol, set triggers for data review, define a quorum, establish guidelines for monitoring the study, and designate a DMC Chair.

All discussions and decisions will be documented in writing. The DMC will advise the study sponsor of its findings in writing.

In the event that a stopping rule for an individual subject is triggered (Section 7.8), the data monitoring committee will meet on an ad hoc basis to review the data and determine whether the clinical trial should be stopped or requires modification in order to proceed safely.

^{**}FDA Grading of Clinical Laboratory Abnormalities (Appendix 4)

The DMC will only meet if a stopping rule for an individual subject is triggered. In the event that a stopping rule is triggered, the DMC will make every reasonable attempt to meet as soon as possible, preferably within three (3) to five (5) business days of the Sponsor being notified of the event, but no later than ten (10) business days. During this period, the DMC will be provided the relevant information regarding the event(s) that triggered the stopping rule in the subject.

In the event that adequate information is not available in the timeframe noted above, the DMC may schedule a second meeting to review additional information regarding the event(s) triggering a stopping rule in an individual subject.

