7.2.4 SAEs, Medically Significant Event and New Onset of Chronic Illness

All SAE, expected or unexpected, medically significant event or new onset of chronic illness occurring between obtaining the subject's written consent to participate in the study and the last study visit will be documented in the eCRF, first in an AE form. For SAE, upon completion of the AE form, and confirmation that the AE is an SAE, the investigator or delegates will be prompted to complete and submit a SAE report form. Follow-up SAE forms may be completed and submitted as needed e.g., if the event outcome, treatment and resolution are not known at the time of the initial report. The follow-up information should contain sufficient detail to allow for a complete medical assessment of the case and an independent determination of possible causality, such as concomitant medications, or other conditions possibly explaining the SAE if any (must be consistent with the medical history recorded at baseline), relevant diagnostic tests, and autopsy report if applicable. All copies of source data attached with the SAE report form will be de-identified to protect subjects subjects' privacy.

In addition, the reports should record: subject unique study ID, age, gender, weight, initial or follow-up report, date of the event, date of report, and individual completing the report.

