7.3 Expedited reporting procedures to study sponsor and pharmacovigilance agent

7.3.1 Serious Adverse Events

SAEs require prompt or immediate reporting to the site Principal Investigator or designates. The site Principal Investigator will be responsible for reporting the SAEs to study sponsor/pharmacovigilance agent as per protocol, and to the IRB/REB if/as required by institutional policies and procedures.

The site Principal Investigator or delegates will complete and submit a SAE form in the eCRF, within 24 hours of becoming aware of the SAE. An E-mail notification of the SAE will be sent automatically to the Medical Monitor/pharmacovigilance agent appointed by study sponsor. The Medical Monitor/pharmacovigilance agent will assess the SAE report and proceed to report to the appropriate regulatory bodies as described in section 7.4.

Once additional relevant information is received, the report should be updated WITHIN 24 HOURS.

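### After its organisational meeting the DMC meets only on an individual stopping rule, so a serious suspected reaction starting more than 7 days after the most recent dose does not itself bring independent review

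*Protocol*

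**What the plan says.** Protocol Section 7.9 sets up an independent DMC. At its organisational meeting the committee is to "set triggers for data review, define a quorum, establish guidelines for monitoring the study". When a Section 7.8 rule is triggered, it meets ad hoc to review the data and "determine whether the clinical trial should be stopped or requires modification in order to proceed safely". The section then restricts this: "The DMC will only meet if a stopping rule for an individual subject is triggered". A second meeting is allowed, but only to look at further information on the same triggering event.

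Section 7.8 lists six criteria that end further vaccination in an individual subject. Each carries a time limit. The broadest is "Any life-threatening event within 7 days after any study injection, regardless of relationship to study vaccine".

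Safety collection runs much longer. Section 7.2.4 covers "All SAE, expected or unexpected, medically significant event or new onset of chronic illness" from consent to the last study visit. Under Section 7.3.1 the Medical Monitor or pharmacovigilance agent "will assess the SAE report and proceed to report to the appropriate regulatory bodies".

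On unblinding, Section 7.7 makes the Medical Monitor responsible for "unblinding of events that meet the study stopping rules, if this is determined to be necessary for evaluation purposes by the data monitoring committee". It continues: "For all other cases, the Medical Monitor will determine on a case-by-case basis if it is necessary to break the blind".

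**The concern.** The two statements in Section 7.9 do not fit together. A committee that sets triggers for data review would be expected to meet when one is reached, yet as written only a Section 7.8 rule can bring it together.

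The stake is who judges a late safety signal. The DMC is the one independent body given the task of deciding whether the trial should stop or change. Suppose a fatal suspected reaction begins 8 days after a first dose. It meets no Section 7.8 criterion, so it does not itself convene the DMC, although other subjects may still be due dose 2 or dose 3. The same applies to a rise in the rate of serious suspected reactions when no single event meets Section 7.8. In both cases DMC review would follow only if some other subject happened to meet a stopping rule.

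**Working it through.** The plan states no figure here, so the check is mainly a comparison of text, followed by a calendar count that limits what may be concluded.

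**Step 1. Time limits of the convening events (Protocol 7.8).**

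| Criterion | Limit after injection |
|---|---|
| Grade 4 post-injection reaction | 7 days |
| Clinically significant systemic reaction | 7 days |
| Grade 4 laboratory abnormality (laboratory sub-study only) | 7 days |
| Grade 3 or 4 hypotension | 24 hours |
| Grade 3 or 4 respiratory reaction | 24 hours |
| Any life-threatening event | 7 days |

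Four rules end at 7 days and two at 24 hours, so 6 of 6 are time-limited. None is based on a count or rate of serious events. The clock restarts with each dose, so the uncovered events are those that start more than 7 days after the most recent dose.

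**Step 2. Other routes to the DMC.**

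| Section | Who receives or acts | DMC named? |
|---|---|---|
| 7.3.1 | Medical Monitor / pharmacovigilance agent; SAE form within 24 hours | No |
| 7.4 | Regulators; also all investigators for the 15-day reports, including rate increases | No |
| 7.5 | Ethics review bodies | No |
| 4.4 | Suspension or termination for unacceptable risk | No |
| 7.7 | DMC may ask for unblinding | Yes, but only for events meeting the stopping rules |

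No route sends a late serious event to the DMC.

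**Step 3. One internal mismatch.** Section 6.2.4.1 allows sub-study samples at 7 days (-3/+7) after a dose, that is days 4 to 14, which is 11 days. The Grade 4 laboratory rule ends at day 7. Days 8 to 14, 7 of the 11 permitted sampling days, fall after it.

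**Step 4. Calendar count, as a limit on the claim.** For one subject dosed on Days 0, 28 and 168, there are 168 days before dose 3 (0 to 167). The 7-day windows are days 0-7 and 28-35: 8 + 8 = 16 days. Outside: 168 - 16 = 152, and 152/168 = 90.5%.

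Across the trial the picture differs. The Study Duration entry (15-18 months including 12 months of follow-up) implies recruitment of 3 to 6 months, about 91 to 183 days. Assume steady enrolment and nominal dosing days. With recruitment of R days, some subject is in a window on days 0 to R+7, 28 to R+35 and 168 to R+175.

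- R = 91: days 0-98, 28-126 and 168-266. Uncovered: 127-167, 41 of 267 days (15.4%).
- R = 91, using the full visit windows in Section 6.3.2 (dose 2 up to +7 days, dose 3 from -7 to +7): covered to day 133 and again from day 161 to day 273. Uncovered: 134-160, 27 of 274 days (9.9%).
- R = 183, nominal days: days 0-190, 28-218 and 168-358. Uncovered: 0 of 359 days.

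Some subject is therefore almost always inside a window. What is restricted is which events convene the DMC, not how often it could meet. None of these percentages measures risk.

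**The case against.** The strongest reply has three parts.

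First, the DMC's own procedures are not in these documents. They may define wider triggers, and a data review need not be a meeting. The organisational meeting itself is not caused by a stopping rule, so the restriction may not be meant literally. This stands only in part. The content of the triggers is indeed unknown. But Section 7.9 expressly provides for the organisational meeting, so that meeting does not loosen the restriction on later ones, and committee procedures could not add meetings without overriding the protocol. Review by correspondence would need late-event data, and Section 7.9 provides only for information on the triggering event.

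Second, late events are already handled. SAE forms are due within 24 hours. Unexpected fatal or life-threatening suspected reactions reach regulators within 7 calendar days. Other serious unexpected suspected reactions, and important rate increases, reach regulators and investigators within 15. Unexpected suspected-related SAEs are unblinded before regulatory reporting (7.7). Eligibility is rechecked before each dose (6.1.2), an SAE is a listed reason to stop vaccine (4.3.2), and the study can be suspended (4.4). All of this stands and lowers the severity. None of it is independent DMC review.

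Third, an ad hoc committee is a proportionate choice for a vaccine marketed in the 14 places listed in Section 1.3.1, with an estimated 500,000 or more people vaccinated across its formulations. That is a fair argument against routine meetings. It does not explain why a trigger set by the committee should be unable to convene it.

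**Conclusion.** The point holds as a gap in the written oversight plan. Following Section 7.9 as worded, a serious suspected reaction starting more than 7 days after the most recent dose, or a rise in the rate of such reactions, does not itself convene the DMC, and Sections 7.3 to 7.5 do not inform it.

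Two stronger readings are tempting and not supported. A reader might infer that late serious events go unmonitored. They do not: other bodies receive and act on them, and once convened for another reason the DMC can still decide at trial level. A reader might also infer from the 90% figure that the committee is out of action for most of the trial. That figure is one subject's calendar. Under the trial-level assumptions above, 0 to 15% of dosing-period days have no subject in a window, and the upper end depends on short recruitment and nominal dosing days.

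The documents give no late-event rate, so the practical consequence cannot be sized. The conclusion rests on reading the restriction in Section 7.9 as written, without sight of the DMC's procedures. It is best classed as a cheap improvement.

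**What to change.** In Protocol Section 7.9, replace the restricting sentence with wording such as:

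*After its organisational meeting, the DMC will meet when a Section 7.8 criterion is met; when a data-review trigger set by the DMC is met; when a serious unexpected suspected adverse reaction, or an important rise in the rate of serious suspected adverse reactions, is reported under Section 7.4, regardless of days since injection; or at the request of the DMC Chair or Medical Monitor. No routine periodic meetings are planned.*

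Add that Section 7.4 reports are copied to the DMC. Section 7.8 needs no change.

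A listing pooled across arms is not proposed for detecting clusters. With 40% of enrolment targeted at age 65 or over and controlled chronic disease accepted, background events are expected, and a pooled listing cannot show an imbalance between arms. The case-by-case route in Section 7.7 is not suitable either, since it breaks the blind subject by subject through a Medical Monitor whom the sponsor appoints. If the DMC wants a cluster by arm, an unblinded person independent of the sponsor's study team should supply it.

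The cost is a protocol amendment with IRB/IEC approval across about 30 sites, which can be bundled with another change, and possibly a few ad hoc meetings. Subjects undergo no extra procedures.
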